### 4.3 Subject and Trial Discontinuation

Subjects may choose to withdraw from this study at any time for any reason without penalty of jeopardizing their health care or loss of benefits to which the subject is otherwise entitled.

Within the provisions of informed consent and good clinical judgment with respect to safety, every attempt will be made to have subjects complete the study. The following are reasons to terminate a subject's participation in the study:

1. Subject experiences an AE that in the judgement of the Investigator poses a significant risk to the subject for continued participation in the study.
2. Subject uses any medication that in the judgment of the Investigator poses a significant risk to the subject for continued participation in the study or that will interfere with the interpretation of the results of the study.
3. Subject becomes pregnant.
4. Significant protocol violation or noncompliance on the part of the subject or the Investigator.
5. Intercurrent illness that requires treatment that is not consistent with the protocol requirements, or intercurrent illness or the associated treatment that in the judgment of the Investigator poses a significant risk to the subject for continued participation in the study.
6. Subject wishes to withdraw for any reason.
7. Sponsor elects to end the study, or the Investigational Site elects to end the study at their site.
8. Any other reason that in the judgment of the Investigator poses unacceptable risk to the subject.

Subjects who withdraw from the study prior to treatment may be replaced. Subjects who are withdrawn and have received at least one treatment will not be replaced. Subjects who discontinue study drug treatment will not be replaced.

Except in cases of emergency, the Investigator should consult with the Sponsor and the Medical Monitor before removing the subject from the study. In some circumstances it may be necessary to temporarily interrupt treatment as a result of AEs that may have an unclear relationship to the IMP. The Investigator should obtain approval from the Sponsor and Medical Monitor before restarting IMPs that were temporarily discontinued for an AE.

In the event that a subject discontinues the study prior to completion, the date the subject is withdrawn and the reason for discontinuation will be recorded in the source documents and eCRF. Although a subject will not be obliged to give his/her reason for withdrawing prematurely, the Investigator will make a reasonable effort to obtain the reason while fully respecting the subject's rights.

All subjects who are randomized and treated (i.e., received any amount of IMP) will be included in the safety analyses. Thus, every effort will be made to contact any subject who fails to attend

any follow-up appointments/contacts, in order to ensure that he/she is in satisfactory health. If a subject withdraws from the study as a result of meeting discontinuation criteria after the start of IMP administration, reasonable efforts should be made to have the subject return for the early withdrawal evaluations ([Section 3.5](#)). Any subject withdrawn due to a suspected IMP related AE should be followed until resolution or stabilization of the event.

If a subject becomes pregnant, IMP will be discontinued immediately, and the subject will be referred to an obstetrician/gynecologist experienced in reproductive toxicity for further evaluation and counseling. The subject will be followed until delivery or other termination of pregnancy for outcome.

Subjects may choose to withdraw authorization to use and disclose their PHI as defined by the HIPAA. Such withdrawal of authorization must be made to the Investigator in writing. Any PHI collected by the Investigator prior to the date of such withdrawal will continue to be used and disclosed.

The Sponsor has the right to terminate this study, and the Investigator/Investigational Site has the right to close the site, at any time, although this should occur only after consultation between involved parties. The Investigator or representative will notify the IRB in writing of a premature termination of a study or closure of Investigational Site or of a temporary halt of the study, including the reason of such an action and will send a copy of the notification to the Sponsor.

Events that may trigger premature termination of a study or closure of an Investigational Site include, but are not limited to, a new toxicity finding, a request to discontinue the trial from a regulatory authority, non-compliance with the protocol, GCP violations, slow recruitment/low enrollment, or change in development plans for the IMP.

If either of the criteria listed below is met, enrollment of new subjects and dosing of ongoing subjects will be temporarily stopped. The Investigator, Sponsor, and the Medical Monitor will discuss whether a lower dose or any additional treatment guidelines should be implemented, or if the trial should be permanently stopped. Any proposed changes to the protocol to address such findings will be submitted for review and approval by the IRB and U.S. Food and Drug Administration (FDA) prior to re-starting the trial.

1. A death within 30 days after IMP administration where there is a reasonable possibility that the drug caused the event;
2. Two Grade 4 AEs where there is a reasonable possibility that the IMP caused the events.

## 5 STUDY TREATMENT (IMP)

### 5.1 Description of Investigational Drug

Active:

Code name: ORMD-0801

Dosage form: 1 soft gelatin capsule administered BID (1 capsule in the morning and 1 capsule at night)

Strength: 8 mg insulin per capsule

Description: API (recombinant human insulin USP), in Oramed's proprietary formulation [SBTI, disodium EDTA, fish oil, aerosil, and TWEEN 80] in capsules.

Placebo control:

Fish oil in capsules, identical in appearance to ORMD-0801, administered BID (one capsule in the morning, prior to breakfast and one capsule at night), daily.

#### 5.1.1 Packaging and Labeling

All study medication will be shipped in bulk. Sufficient study medication will be distributed to cover the time between visits. The Investigational Site pharmacist will be responsible for dispensing the appropriate treatment period study treatment based on the randomization schedule.

Study medication will be dispensed to the site with instructions for when treatment can be administered.

The treatment packages will be labeled with the following information:

- Study number
- Patient ID
- Bottle ID
- Dosage Form/Content
- Directions for use, including route of administration
- Number of capsules in package
- Storage conditions
- Instructions to "keep out of reach of children"
- Caution: New Drug – Limited by Federal (or United States) law to investigational use.
- Name of Sponsor

A label with the identical information will be made available for drug accountability purposes.

#### 5.1.2 Storage and Handling

All IMP must be kept in an appropriate, secure area to prevent unauthorized access. All IMP is to be shipped under refrigerated conditions and stored at controlled temperature (36 to 46°F; 2 to 8°C). Excessive humidity should be avoided. Storage conditions will be monitored, and appropriate monitoring logs maintained as source data. Deviations from the established

temperature, as well as the occurrence of excessive humidity, should be documented, and the Sponsor should be notified.

IMP should be handled, using proper procedures as defined by Investigational Site standard operating procedures (SOPs) for Investigational Drugs. IMP will be returned or destroyed according to instructions provided by Oramed Ltd. Drug destruction procedures and documentation must be retained at the site.

Investigator will be supplied with a sufficient amount of study medication in order to provide each subject with sufficient treatment. Site will document their inspection of shipments of study medication and notify the Sponsor of any breakage, shortage, or other adverse shipment events.

## 5.2 Randomization

This is a double-blind, randomized, placebo-controlled study. Adult male and female subjects with NASH and type 2 DM will be competitively enrolled at all study sites. Approximately 36 subjects will be randomized in a 2:1 ratio to either ORMD-0801 8 mg BID or to matching placebo.

Integrium, LLC will generate and implement the randomization procedures for this trial. A computer-generated randomization schedule will be used for assigning the treatment groups. The Investigational Site pharmacist will follow this randomization schedule to dispense the appropriate study treatment.

## 5.3 IMP Administration

### 5.3.1 Week 0 to Week 12 (Visit 3 to Visit 8)

The treatment regimen will consist of a soft gelatin capsule containing 8 mg insulin, and 75 mg SBTI. Sufficient quantity of medication will be dispensed to last until the next nominal clinic visit. ORMD-0801 morning treatment will be administered in clinic during Visits 3, 6 and 7. Subjects will receive either 8 mg ORMD-0801, 1 capsule twice a day (once in the morning approximately 30 to 45 minutes prior to breakfast and no later than 10 AM, and once at night between 8 PM to Midnight and no sooner than 1 hour after dinner) or matching placebo.

At Visits 2 (Placebo Run-in), 3, 6, and 7 blood samples and weights will be taken prior to morning dosing in clinic, followed by a small snack after 30 to 45 minutes.

## 5.4 Dose Modifications

This study does not include any planned dose modifications. Subjects will be administered IMP orally at the assigned dose level unless discontinuation criteria as defined in [Section 4.3](#) are met.

## 5.5 Measuring Subject Compliance

Dosing compliance will be assessed through a count of unused study medication during clinic Visit 3 to Visit 8.

## 5.6 Drug Accountability

In accordance with current GCP, the Investigational Site will account for all IMP supplies. Details of receipt, storage, administration, and return or destruction will be recorded in the Investigational Drug accountability record according to the SOP of the Investigational Site. Copies of the Investigational Drug accountability record will be provided to the Sponsor.

IMP will only be dispensed to subjects enrolled in this protocol, and only as directed by this protocol. Administration of IMP will be accurately recorded in each subject's source documents and eCRF. Study participants will be dispensed sufficient quantities of study treatment to last until the next nominal clinic visit. Study participants will be asked to return all unused study medication for accountability at each clinic visit. Compliance with study medication is monitored and recorded by site personnel by counting the remaining study medication.

At the conclusion of the study, study drug supplies (including partially used packages) will be returned or destroyed according to instructions provided by Oramed Ltd. Drug destruction procedures and documentation must be retained at the site.

## 5.7 Concomitant Medications and Supplements

All prior medications and supplements taken within 30 days prior to the first dose of IMP and concomitant medications and supplements will be recorded in the subject's source documentation and in the eCRF.

Any concomitant medication use will be evaluated on a case-by-case basis by the Investigator. If a subject requires the use of any medications, the Investigator will contact the Sponsor and the Medical Monitor to discuss the subject's continued participation in the study. In the event of an emergency, subjects will be treated at the discretion of the Investigator according to acceptable community standards of medical care.

## 5.8 Behavioral Restrictions

Subjects should arrive following a minimum 10-hour fast and must not take any food prior to scheduled dosing as described in the study design. Water intake will be unrestricted. All subjects will continue with their regular diet.

Excessive caffeine use (i.e., more than five cups of caffeinated beverages per day) will not be allowed from Screening through Visit 8. Excessive alcohol use or binge drinking will be discouraged during the study, and alcohol will be prohibited 72 hours prior to each visit. Subject should not use any recreational or illicit drugs throughout the study.

Subjects will also be asked to refrain from any unusual or unaccustomed vigorous exercise during the course of the study.

## 6 STUDY PROCEDURES AND ASSESSMENTS

### 6.1 Informed Consent

According to the ICH guideline for GCP (E6) and all institutional local, state, and federal laws, the Investigator will obtain and document informed consent for each subject screened for this study. All subjects will be informed in writing of the nature of the protocol and Investigational Drug, its possible hazards, and their right to withdraw at any time, and will voluntarily sign a form (ICF) indicating their consent to participate in the study prior to the initiation of study procedures. The subject's medical record should contain written documentation indicating that informed consent was obtained. The ICF must be reviewed and approved by the Investigator's designated IRB and by Oramed Ltd. designee prior to its use. Refer to [Section 11.1.4](#) for further details regarding informed consent.

### 6.2 Demographics, Medical History and Prior Medications

At Screening, demographics (sex, age, race and ethnicity), a complete medical history and social history, including smoking, caffeine, alcohol, and drug use, will be collected by subject interview. Medications and supplements, recent blood donations, illnesses, and participation in other Investigational Drug trials or clinical trials will also be recorded.

### 6.3 Study Endpoints

The primary endpoint of this trial will evaluate safety of ORMD-0801 in patients with nonalcoholic steatohepatitis (NASH) and type 2 DM.

Secondary endpoint will evaluate the effectiveness of ORMD-0801 in reducing liver fat content in patients with NASH and type 2 DM by measuring the final and baseline differences in the MRI-PDFF.

### 6.4 Efficacy Assessments

Fat content in the liver will be assessed by measuring the final and baseline differences in the MRI-PDFF results. Images generated from the MRI-PDFF scans will be submitted for central reading.

### 6.5 Safety Assessments

#### 6.5.1 Weight and Height

Height will be measured, and BMI will be calculated at Screening only with the subject wearing no shoes. Weight will be measured at all visits in fasting conditions when possible (on visits when subject is required to fast). The subject will be clothed while being weighed, but should remove shoes, coats, jewelry and other accessories (refer to [Table 1](#)).

#### 6.5.2 Vital Signs

Vital signs, including seated systolic/diastolic blood pressure (SBP/DBP), heart rate and oral temperature, will be recorded where indicated in [Table 1](#). Vital signs will be measured after the subject has been sitting for at least 5 minutes in a quiet environment and prior to any blood draw

that occurs at the same time point. The recorded seated SBP/DBP value will be the mean of two measurements taken 2 minutes apart and always using the non-dominant arm.

### 6.5.3 Physical Examination

A complete physical examination will be performed at Screening and Visits 3 and 8 (refer to [Table 1](#)). At the Investigator's discretion, an additional physical exam may be performed during the End-of-Study/Early Termination (Visit 9). The physical examination will include the following organ or body system assessments: skin; head, eyes, ears, nose, and throat; thyroid; lungs; cardiovascular; abdomen (liver, spleen); lymph nodes; and extremities, as well as an abbreviated neurological examination.

### 6.5.4 12-Lead ECG

A 12-lead ECG will be performed at Screening as indicated in [Table 1](#). At the Investigator's discretion, an additional ECG may be performed at the End-of-Study/Early Termination (Visit 9). The 12-lead ECG will be recorded after the subject has been resting at least 5 minutes in the supine position in a quiet environment. ECGs will be read for QT and QTc (Fridericia's) intervals and clinically significant abnormalities.

### 6.5.5 Clinical Laboratory Tests

Blood for clinical safety laboratory assessments will be collected and processed using standard procedures at Screening and on Visits 3, 6, 7, 8 and 9 and on any unscheduled visit if the investigator deems it necessary, as indicated in [Table 1](#). A local laboratory will perform all clinical laboratory tests. In the event of abnormal clinical laboratory values, the Investigator will make a judgment whether or not the abnormality is clinically significant.

#### 6.5.5.1 Clinical Safety Laboratory Tests

The clinical safety laboratory tests will include the following hematology and serum chemistry tests:

- Hematology
  - Hemoglobin
  - Hematocrit
  - RBC
  - WBC (total count and differential count)
  - Platelets Count
  - Mean Platelet Volume (MPV)
  - MCV
  - MCH
  - MCHC
  - RDW
  - Neutrophils (absolute value and %)
  - Bands (ABS CNT)
  - Bands
  - Lymphocytes (absolute value and %)
  - Monocytes (absolute value and %)
  - Eosinophils (absolute value and %)

- Basophils (absolute value and %)
- RBC Morphology
- Serum Chemistry
  - Sodium
  - Potassium
  - Glucose
  - BUN
  - Creatinine
  - BUN/Creatinine
  - Chloride
  - Calcium
  - Protein
  - Albumin
  - Globulin (total)
  - A/G Ratio
  - SGOT (AST)
  - SGPT (ALT)
  - Bilirubin (total)
  - Alkaline Phosphatase
  - CO2
  - Creatine Phosphokinase (CPK)
  - Blood lipids: Total cholesterol, LDL, HDL, Triglycerides
  - Thyroid stimulating hormone (TSH, screening only)

Urinalysis is not performed in this study.

#### 6.5.6 Additional Bloodwork

In addition to the blood tests listed above, viral serology (HCV-Ab, HBsAg, HBcore-total, HBs Ab, and anti-HIV Ab), HbA1c, and adiponectin will be measured as indicated in [Table 1](#). Adiponectin samples will be shipped to a Central Laboratory in Israel.

#### 6.5.7 Fasting Blood Glucose and Insulin Monitoring

During the study, both fasting finger stick glucose and laboratory fasting plasma glucose will be obtained at time points stated in [Table 1](#). Fasting blood insulin will be used to determine HOMA estimates.

#### 6.5.8 Pregnancy Test

A serum pregnancy test will be performed for WCBP at Screening (Visit 1). A urine pregnancy test will be performed for WCBP at Visit 2 and Visit 3 (refer to [Table 1](#)).

FSH testing (if not available) to confirm menopause will be performed at Screening for women who have had more than 24 months since their last menstrual cycle, who are younger than 55 years old, and who are not surgically menopausal.

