#### 3.4.1 Visit 3 (Week 0, Days 0±4)

Subjects will report to the clinic in the morning following a 10-hour fast prior to taking morning medication. The following procedures will be performed:

- Review of concomitant medication;
- Complete physical examination;
- Measurement of weight;
- Collection of unused placebo medication;
- Dispense 1 bottle of ORMD-0801 medication with instructions for administration. Subjects will receive either 8 mg ORMD-0801, 1 capsule twice a day (once in the morning approximately 30 to 45 minutes prior to breakfast and no later than 10 AM, and once at night between 8 PM to Midnight and no sooner than 1 hour after dinner) or matching placebo;
- Perform medication compliance check;
- Measurement of vital signs (SBP/DBP, heart rate and oral temperature)
- Collection of fasted blood samples for clinical laboratory evaluations (see [Section 6.5.5.1](#) for a complete list of tests performed):
  - Serum Chemistry including liver function tests (LFTs) and blood lipids;
  - Hematology;
- Urine pregnancy test (women of childbearing potential/WCBP only) prior to active dosing;
- Measurement of fasting blood glucose and fasting insulin for HOMA estimates;
- Review/Dispense diaries for each week for subjects to self-monitor fasting morning blood glucose;
- Self-monitored fasting morning blood glucose (finger-stick) recorded in the patient diaries 3 days weekly in the morning;
- Adiponectin test;

- CAP-Fibroscan;
- AEs/SAEs assessment;
- Subjects will be administered morning treatment dose in clinic followed by a small snack after 30 to 45 minutes;
- Remind subjects to arrive for Visit 4 in 1 week.

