## Table 1 Footnotes

-  Prior and concomitant medications will be reviewed at Screening. Concomitant medications will be reviewed through Visits 2-9.
-  Only if investigator deems necessary.
-  Height measurement and BMI calculation will be performed at Screening only. Weight will be measured as indicated.
-  Serum pregnancy test will be performed at Screening (Visit 1). Urine pregnancy test will be performed at Visit 2 and Visit 3.
-  Blood samples taken prior to dosing in clinic and snack provided after 30-45 minutes at Visit 2, 3, 6, and 7.
-  Study medication will be dispensed and collected at Visits 2-8 and collected at End-of-Study/Early Termination Visit.
-  Vital signs (blood pressure, heart rate, oral temperature). Vital signs will be measured in the sitting position after at least 5 minutes of rest.
-  Serum Chemistry: Sodium, Potassium, Glucose, BUN, Creatinine, BUN/Creatinine, Chloride, Calcium, Protein, Albumin, Globulin (total), A/G Ratio, SGOT (AST), SGPT (ALT), Bilirubin (total), Alkaline Phosphatase, CO2, Creatine Phosphokinase (CPK), Total cholesterol, LDL, HDL, Triglycerides, Thyroid Stimulating Hormone (TSH, screening only). Hematology: Hemoglobin, Hematocrit, RBC, WBC (total count and differential count), Platelets Count, Mean Platelet Volume (MPV), MCV, MCH, MCHC, RDW, Neutrophils (absolute value and %), Bands (ABS CNT), Bands, Lymphocytes (absolute value and %), Monocytes (absolute value and %), Eosinophils (absolute value and %), Basophils (absolute value and %), RBC Morphology. Urinalysis is not performed in this study.
-  Fasting blood glucose and insulin will be used to determine Homeostasis Model Assessment (HOMA) estimates. During an Unscheduled Visit only fasting blood glucose will be collected, if investigator deems necessary.
-  Self-monitoring (finger-stick) of fasting blood glucose will be required 3 days weekly in the morning, before breakfast, and recorded in patient diaries.
-  HCV-Ab (hepatitis C virus antibody), HBsAg (surface antigen of the hepatitis B virus), HBcore-total (total hepatitis B core antibody), HBs Ab (hepatitis B surface antibody), anti-HIV Ab (human immunodeficiency virus antibody).

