#### Inclusion Criteria

1. Male or female aged 18-70 years.
2. BMI  $\geq 25$ .
3. Known type 2 DM according to American Diabetic Association (one of the three needed): Fasting Plasma Glucose  $\geq 126$  mg/dl or 2h postprandial (PG) following 75g OGTT  $\geq 200$  mg/dl or HbA1c  $> 6.5\%$  or on treatment with metformin only or metformin in addition to no more than two of the following medications sulfonylurea, DPP-4 inhibitors, GLP-1 receptor agonists, Thiazolidinediones (TZDs).
4. Diagnosis of NAFLD by non-invasive determination of hepatic steatosis grade S1, defined as hepatic steatosis  $> 8\%$ , by MRI- PDFF and CAP FibroScan  $\geq 238$  dB/m.
5. Liver enzyme abnormalities: ULN  $\leq 5$  times.
6. Fibrosis score  $1 \leq F \leq 3$  as defined by FibroScan measurement (Liver stiffness measurement, LSM) of  $6 \leq \text{LSM} \leq 12$  kPa.
7. Signature of the written informed consent.
8. Negative serum pregnancy test at study entry for females of childbearing potential.
9. Women of childbearing potential must have a negative urine pregnancy test result prior to the start of the run-in period and initiation if active dosing. Males and females of childbearing potential must use two methods of contraception (double barrier method), one of which must be an acceptable barrier method from the time of screening to the last study visit (22 weeks). Barrier methods of contraception include male condoms plus spermicide, diaphragm with spermicide plus male condom, and cervical cap with spermicide plus male condom. Acceptable methods of birth control include abstinence, oral contraceptives, surgical sterilization, vasectomy, the contraceptive patch, and the contraceptive ring. If a subject is not usually sexually active but becomes active, he or his partner should use medically accepted forms of contraception. Sperm donations will not be allowed for the duration of the study and for 90 days after the last dose of study drug.  
Females of non-childbearing potential are defined as postmenopausal who a) had more than 24 months since last menstrual cycle with menopausal levels of FSH (FSH Level  $> 40$ ), b) who are surgically menopausal (surgical sterility defined by tubal occlusion, bilateral oophorectomy, bilateral salpingectomy or hysterectomy).

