#### 7.5.2.1 Pregnancy Reporting

If the subject or partner of a subject participating in the study becomes pregnant during the study or within 30 days of discontinuing study medication, the Investigator should report the pregnancy to Oramed within 24 hours of being notified. The Exposure In-Utero form to the Investigator for completion.

The subject or partner should be followed by the Investigator until completion of the pregnancy. If the pregnancy ends for any reason before the anticipated date, the Investigator should notify the Sponsor. At the completion of the pregnancy, the investigator will document the outcome of the pregnancy. If the outcome of the pregnancy meets the criteria for immediate classification as an SAE (i.e., postpartum complication, spontaneous abortion, stillbirth, neonatal death, or congenital anomaly), the Investigator should follow the procedures for reporting an SAE.

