### 7.6.1 Potential Adverse Events Associated with ORMD-0801

Hypoglycemia and associated symptoms (e.g., weakness, dizziness, shakiness, increased sweating, palpitations, or confusion), have been associated with insulin administration, including ORMD-0801. Animal reproductive studies have not been conducted with ORMD-0801. It is not known whether ORMD-0801 can cause fetal harm when administered to a pregnant woman. It is also not known whether this product is excreted in human milk. Pregnant or breastfeeding women are excluded from this study.

Long-term animal studies have not been completed to assess whether ORMD-0801 impairs fertility.

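### No pregnancy test is scheduled once randomized dosing begins, although pregnancy must stop the drug at once, and contraception ends about two months before the sperm-donation bar in the same criterion

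*Combined protocol and SAP*

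**What the plan says.** **Testing.** Women of childbearing potential have a serum test at Screening. After that, section 6.5.8 says "A urine pregnancy test will be performed for WCBP at Visit 2 and Visit 3". Footnote 4 to Table 1 agrees: "Urine pregnancy test will be performed at Visit 2 and Visit 3". The Visit 3 procedure list (section 3.4.1) places that test before the first randomized dose: "Urine pregnancy test (women of childbearing potential/WCBP only) prior to active dosing". The lists for Visits 4 to 9 and for unscheduled visits (sections 3.4.2 to 3.6) contain no pregnancy test.

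**Action on pregnancy.** Section 4.3 lists pregnancy as a reason to end participation and adds: "If a subject becomes pregnant, IMP will be discontinued immediately". Section 7.6.1 reports that there are no animal reproductive studies, says "It is not known whether ORMD-0801 can cause fetal harm when administered to a pregnant woman", and treats pregnant women as excluded.

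**Periods after dosing.**
- Contraception: inclusion criterion 9 requires it of men and of women of childbearing potential "from the time of screening to the last study visit (22 weeks"). Section 3.2.1 gives the same end point, Visit 9.
- Sperm donation, also in criterion 9: "Sperm donations will not be allowed for the duration of the study and for 90 days after the last dose of study drug".
- Pregnancy reporting (section 7.5.2.1): a subject or partner who "becomes pregnant during the study or within 30 days of discontinuing study medication".

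**The concern.** The rule in section 4.3 works only if someone learns of the pregnancy. After Day 0 no scheduled procedure is designed to find one. A woman who conceives early in treatment could go on taking a product of unknown fetal risk until she suspects a pregnancy and reports it. The trial, whose primary objective is safety, would also have no planned confirmation that its women were not pregnant while dosed.

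The periods after dosing raise a second, separate question. Contraception ends at a visit, whereas the sperm-donation bar and the reporting window run from the end of dosing. Under the nominal schedule, a man 29 days after his last dose may not donate sperm but is no longer required to use contraception, both under criterion 9. A subject who leaves the study early may have no visit left at which a still-reportable pregnancy would come to light.

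**Working it through.** This is calendar arithmetic on the visit schedule. No power or sample-size figure is involved.

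**Inputs**
- Screening: up to Day -42 (section 3.2).
- Visit 3, first randomized dose and last pregnancy test: Day 0 (section 3.4.1).
- Visit 8, end of treatment: Day 84 ± 4, with no drug dispensed (section 3.4.6).
- Visit 9, last study visit: Day 112 ± 4 (section 3.5).
- Reporting window: 30 days after stopping the drug (section 7.5.2.1).
- Sperm-donation bar: 90 days after the last dose (criterion 9).

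**The plan's own figure.** (112 − (−42)) / 7 = 154 / 7 = 22 weeks. This reproduces criterion 9 exactly and confirms that its end point is Visit 9 with screening at its longest.

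**Treatment time without a scheduled test.** 84 − 0 = 84 days. At two capsules a day, 84 × 2 = 168 capsules.

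**Contraception cover after the last dose, completers.** Cover = day of Visit 9 − day of last dose, taking the last dose at Visit 8. Shortfall = window − cover.

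| Last dose | Visit 9 | Cover (days) | Shortfall against 30 | Shortfall against 90 |
|---|---|---|---|---|
| Day 84 | Day 112 | 28 | 2 | 62 |
| Day 80 | Day 116 | 36 | −6 (6 days beyond) | 54 |
| Day 88 | Day 108 | 20 | 10 | 70 |

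If the last dose is the evening before Visit 8 (Day 83), cover is 112 − 83 = 29 days and the shortfalls are 1 and 61.

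**Early leavers.** Section 3.5 has subjects discontinued from the study complete the End-of-Study evaluations at that time. If that visit is their last and falls on the day of the last dose, cover is 0 days and the shortfalls are 30 and 90. These are upper limits. Section 4.3 asks withdrawn subjects to return for the evaluations, which may be some days later.

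**The case against.** **Other safeguards exist.** Three negative tests precede randomized dosing, two contraceptive methods are required, adverse events are assessed at every visit with open-ended questions (section 7.1), and section 3.6 allows safety laboratory work at unscheduled visits. A reader might infer that the plan has no means of learning of a pregnancy, and that would go too far. What stands is narrower. Pregnancy tests are not in the section 6.5.5.1 laboratory list, and the 24-hour report in section 7.5.2.1 runs from when the investigator is notified. Contraception lowers the risk but does not detect its failure, for which the protocol itself plans.

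**The windows serve different purposes.** The 30 days are a reporting window and the 90 days a donation bar. Neither is stated as a contraception period, and neither sets one for women. Rules with different purposes may have different lengths, so a reader should not call all three contradictory. The real tension is within criterion 9, which treats a man's sperm differently for donation and for contraception over about two months without a reason.

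**The 30-day gap is small for completers.** One might infer that contraception ends well before the reporting window closes. For completers the nominal gap is 2 days and can vanish within the visit windows. The inference fits only subjects who leave the study early.

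**Stopping the drug is not leaving the study.** Section 3.7 has subjects taken off drug for glucose values continue with the remaining visits (if possible, in the case of high values), so their contraception period continues. The 22 weeks in criterion 9 also leave it unclear whether an early leaver's obligation ends on the day of leaving.

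**Size.** One might count 112 of 154 days (73%) as untested. That adds 28 days off drug, when there is nothing to stop, and assumes the longest screening. The relevant figure is the 84 treatment days.

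**Conclusion.** The point holds in two parts.

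1. No pregnancy test is scheduled on treatment or at its end. For 84 treatment days, no scheduled procedure is aimed at detecting the event that section 4.3 says must stop the drug at once. This follows from the text and needs no assumption.
2. The contraception end point is not aligned with the other periods. It falls about 62 days (54 to 70) before criterion 9's own sperm-donation bar lifts. Against the 30-day reporting window, completers range from 10 days short to 6 days beyond (nominally 2 short), while early leavers may be up to 30 days short. These figures assume a last dose at Visit 8 and that the obligation ends at the last visit attended.

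The number of women affected cannot be estimated. About 36 subjects aged 18 to 70 are randomized 2:1, so about 36 × 2/3 = 24 receive active drug, but the number of childbearing potential is not given. This is a subject-protection and safety-data gap worth closing. It does not bear on the efficacy analysis.

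**What to change.** 1. Reconcile section 6.5.8, Table 1 and its footnote 4 with sections 4.3 and 7.6.1, so that the schedule provides a way to detect pregnancy during treatment at visits already planned. Which visits is for the sponsor to decide.
2. Reconcile section 3.2.1, inclusion criterion 9 (in the synopsis and section 4.1) and section 7.5.2.1, so that the contraception, sperm-donation and pregnancy-reporting periods and the dates from which they run are consistent, or their differences are justified. State explicitly what applies to subjects who leave the study early. The sponsor should choose the periods.

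The cost is a few urine tests per woman of childbearing potential at existing visits, plus amendment and consent-form wording.
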